Sources of Materials Participants will be recruited from the community via public notices at community centers (i.e., YMCA, rec centers, libraries, etc.), local newspapers, internet-based resources (e.g., Craig's List or Facebook), or through community support groups for families coping with mental illness. We plan to balance our sample by gender and ensure that it will reflect the demographic characteristics of the Hartford region. Research information includes psychiatric interview results, ratings made by participants on self-report questionnaires, medical history, family psychiatric history, MRI measures of brain structure and function collected during different neurocognitive tasks, electrodermal and eye-tracking responses during fMRI task completion, and identifying information such as name, DOB and contact information.

Potential Risks and Protection Against Risks The risks in this study involve procedures performed solely for the purposes of research. These risks include: psychological ratings, fMRI involving exposure to emotion-eliciting images, skin conductance recordings, eye-tracking, discomfort from interviewing, urinalysis, risks related to privacy/confidentiality of records, and unanticipated risks.

Psychological Ratings: Patients may find the battery of psychiatric and neuropsychological tests tedious and boring, or intrusive. If the former, brief breaks will be given during assessment. The latter concern is addressed through use of trained interviewers who have experience discussing sensitive material with clinical research subjects. However, if a subject finds a topic too uncomfortable or sensitive, those questions will be skipped, or with severe reactions, subjects will be debriefed and reminded they can discontinue participation without penalty, if necessary.

FMRI: The FDA has approved the MRI system and the scanning protocols to be used. The MRI scanning procedure in a 3 Tesla system is safe in normal healthy humans. However, subjects who could suffer potential risks from the MRI scanning procedure include those with metal implants (pacemaker, metal rods, bone screws, orthodontics, metal flakes from metalworking). Subjects are told during the informed consent process about the need to carefully screen for metal implants or any other exposure to metal in the body. Subjects who could potentially suffer harm will be screened for metal prior to scanning using a HH Radiology Department screening checklist, and on the day of the MRI will change clothes prior to entering the MRI suite, be scanned for metal using a whole-body ferromagnetic scanner, and be verbally checked by the MR technologist performing the scan. Although there is no proven harm to developing fetuses, women will be screened for pregnancy before scanning. Urinalysis for a one-step pregnancy test is conducted on the scan day to ensure that female participants are not pregnant. Participants with claustrophobia may experience some anxiety symptoms, and will be discouraged from participating. Subjects who feel claustrophobic during the experiment will be encouraged to notify experimenters at any time to discontinue scanning. There are no known risks associated with the visual or auditory stimuli presented during recording of event-related fMRI. All structural MR results are reviewed by Hartford Hospital Radiology staff and a brief clinical report prepared if there seems to be a need for more in depth evaluation. Any indication of pathology/abnormality is communicated to Co-PI [name] (a licensed psychiatrist), who then will order a full clinical MR for the participant. If participants cannot assume the cost of the MR, one is provided to them by the Olin NRC. This procedure ensures that any

risk to health can be identified and proper clinical planning can be done.

Emotional Stimuli During MRI: The IAPS stimuli to be used in this project are well-known to include images of a graphic or sexual nature. We have used such stimuli in previous NIH- and foundation-funded projects (i.e., R01 MH102854, K23 MH070036 and a recent grant from the American Foundation for Suicide Prevention) to probe emotional neural systems. We do not utilize any erotica stimuli at all. The informed consent procedure carefully and explicitly discusses the issue of image content, and offering several examples of stimuli similar to those used in the experimentation. They also are reminded immediately before fMRI that they can discontinue at any time during the experimentation without penalty and still receive compensation for that part of the research. After fMRI, participants are debriefed, which includes initiating a discussion of their overall reaction to the experiment, how the stimuli made them feel, whether they have any questions or problems that they would like to talk about further, etc. Note, our previous experience using tasks that include IAPS stimuli for fMRI assessment in >200 adolescent and young adult participants have never met with any unforeseen, negative reaction after using these procedures.

Skin Conductance Recording During MRI: Risks of physiological recording during MRI include problems related to ferromagnetic equipment being introduced into the MR environment, induced voltages, and radiofrequency (RF) heating ¹³². The Biopac electrodermal recording devices we use for MR are classified as MR conditionally safe by the American Society for Testing of Materials ¹³³. During scanning, time-varying magnetic fields are generated by the gradient coils and RF transmitter, which induce voltages across any conductive loops that can possibly stimulate nerves or heat tissue. These risks are reduced by ensuring that MRI-approved electrodes will be placed between 3-5 cm apart in a configuration that avoids loops, "S" or "U" shapes. Electrode leads will not be twisted and none of the radio-translucent, MRI-compatible wires on SCR-recording electrodes cross on the body. Electrode wires will be run out of the chamber bore in the straightest line possible. After electrode setup with the patient supine in the MR, all SCR wires will be secured with surgical tape at several locations (min 1' apart) to ensure that casual body movement during the ~1 hour MRI session will not displace them. A blanket will cover each participant to ensure wires do not touch the skin. All electrodes will be checked to ensure close contact with the skin (including use of conductive gel) so that air gaps will not break the electric pathway to build up heat at the electrode center and cause burns. Participants are reminded before and periodically during MRI to report any heating or tingling sensations, which will prompt MR staff safety checks of the SCR recording equipment setup.

Infrared Eyetracking During MRI: The Eyelink® 1000 Fiber Optic eyetracking system is approved for use within an MRI environment. The device conforms to numerous international safety standards (e.g., IEC 60825-1, the Safety of Laser Products standard) which covers laser and LED devices. The Eyelink 1000 is classified as a Class 1 LED device, the highest safety certification, which states that it is "safe under reasonably foreseeable conditions of operation, including the use of optical instruments for intrabeam viewing." Class 1 classification is similar to that granted for door motion sensors, TV remotes, etc. Therefore any risks of IR exposure to the eye are minimal. Moreover, IR camera use will be limited to <1 hour throughout the entire MRI experiment.

Videotaped Interview: Some participants may be uncomfortable with the idea of being videotaped during interviews or with research staff having access to their medical files. These study procedures are explained in detail during informed consent procedures so that subjects may make an informed decision whether to participate in the study. To assure the confidentiality and protection of participants with respect to videotaping, videos are stored in digital format and are directly uploaded to a secure, HIPAA-compliant database at the Olin NRC immediately following interview; any local copies of the file are destroyed.

Audiotaped Task Debriefing Responses: All digitally recorded responses collected during the task debriefing procedure will be uploaded onto a computer and saved as an electronic file to be transcribed. Linguistic transcription will be stored on the same secure, HIPAA-compliant database as the videotaped interviews. All electronic files will be destroyed within 6 years following completion of the study.

Urine Collection: Urine specimens are collected to test menstruating females for pregnancy and to monitor unreported substance use prior to MRI scanning and therefore serve as safeguards to participants. It adds no

risks other than those normally associated with providing a specimen in a private bathroom.

Psychological status: During the course of the evaluation, it is possible that some participants may express either suicidal or homicidal ideation or intent. During consent, potential participants are advised that these issues will be cause to break confidentiality to ensure the safety of the participant or others. The Olin NRC has established procedures to escort participants to the Hartford Hospital Emergency Department psychiatric intake if necessary, or to Children's Hospital ED (which is contiguous with Hartford Hospital/The Institute of Living campus on the same city block, roughly the same distance from the Olin NRC as Hartford Hospital's ED). If study personnel ascertain that participants have increased risk to self or others, the study PI will contact the participant's treatment provider, if any, or police (if necessary). If an unmet treatment need is discovered during the course of psychiatric assessment, study staff under direction of the Principal Investigator will recommend further treatment to the participant. The Olin NRC maintains an updated list of both IOL and non-IOL community practitioners for most psychiatric or substance disorder treatment services. However, study personnel cannot break confidentiality to ensure that participants seek treatment for unmet treatment needs if there is not an imminent danger to self or others. The final exception is that researchers are mandated reporters of child abuse to the CT Department of Children and Families. This role also is explained to participants during informed consent.

Unanticipated risks: Any experiment may involve risks that we cannot predict or anticipate. Participants will be told of any important new information that might affect their decision to continue in the study. In addition, the IRB at Hartford Hospital will be notified if any new risks are identified.

Confidentiality: Confidentiality risks will be minimized by using coded records and by storing signed consent forms in double-locked file cabinets in a secure area of the Olin NRC. Electronic records are kept in HIPAA-compliant databases, with secure, user account/password-controlled access to specific records. All procedures are fully-HIPPA compliant and approved by HH Research Administration. All information and data concerning volunteers are confidential and never released to anyone outside of the project without the volunteer's written authorization. The identity of participants is never revealed in research reports.

Adequacy of Protection Against Risks

Informed Consent Informed consent is obtained in writing from all volunteers prior to research participation by a trained research staff. Informed consent meetings will always include a trained research staff member and the potential participant. The detailed consent form will be read to and discussed with these persons. They will be given several opportunities to ask questions and will have the option to watch movies of the laboratory procedures before signing the consent. Prior to agreeing to be in study, it is reinforced that participants can discontinue at any time without prejudice and that questions at any time are encouraged. All potential participants are offered an opportunity to review Hartford Hospital's Patient Bill of Rights and given phone numbers of Olin NRC faculty and disinterested third-party Hartford Hospital officials who oversee research activities or advocate patient rights if there are any complaints. Understanding of study procedures is ascertained by the potential participant's ability to repeat back the procedures and the risks involved in their own words. Any doubts about a potential subject's willingness to participate and their understanding, the PI will opt to exclude the subject.

Potential Benefits of the Proposed Research to the Subjects and Others / Importance of the Knowledge to be Gained Although a substantial investment of time and effort will be required of research participants for clinical interviewing, ER training, and MRI scanning, these methods are fairly non-invasive with regard to importance of information obtained. Such information is routinely collected in clinical research. Appropriate safeguards are in place to protect the well-being and confidentiality of subjects who agree to participate in the study. Furthermore, participants will be compensated monetarily for their time to a degree that does not offer an undue incentive for their cooperation. Therefore, we judge the risks and the intrusion to subjects to be minimal. The scientific benefits of the planned study are high, given the scientific importance of understanding the neurobiology of emotion regulation network changed following ER training. With the safeguards in place as described above, we believe the risks of the study are low. The risk-benefit ratio appears, therefore, to be favorable.

Data Safety and Monitoring Plan Whether or not this study should be considered a clinical trial is debatable. On the one hand, we will randomize participants into conditions and train them in how to regulate their emotions with separate tactics. Moreover, we are specifically recruiting a sample who will range from having mildly-elevated depression/anxiety symptoms to those who might meet DSM 5 diagnostic criteria for MDD or anxiety disorders. However, we purposefully are not employing any standardized treatment protocol in favor of using a “bare-bones” training-based intervention that provides guided practice on specific ways to regulate negative affect. We will not present this study opportunity to potential participants with any expectation that by the end of the study they will have achieved any relief for any mood or anxiety problems. Unless directed by the IRB to construct a more formal DSMP, we plan to follow standard Hartford Hospital adverse event reporting guidelines, which require reporting within 24 hours to the hospital Research Administration and Institutional Review Board any serious adverse event (i.e., serious injury or death related to the investigation) and within 7 days for minor adverse effects. However, if a DSMP typically is deemed appropriate by the IRB, we will formulate one that is appropriate to the perceived low-risk entailed in this experimental protocol.

References

1. Gross, J.J., *Antecedent- and response-focused emotion regulation: divergent consequences for experience, expression, and physiology*. Journal of Personality and Social Psychology, 1998. **74**(1): p. 224-37.
2. Gross, J.J., & Thompson, R.A., *Emotion regulation: Conceptual foundations*, in *Handbook of Emotion Regulation*, J.J. Gross, Editor 2007, Guilford Press: New York, NY. p. pp. 3-24.
3. Gyurak, A., J.J. Gross, and A. Etkin, *Explicit and implicit emotion regulation: a dual-process framework*. Cogn Emot, 2011. **25**(3): p. 400-12. **PMCID**: 3280343
4. Ochsner, K.N. and J.J. Gross, *The neural architecture of emotion regulation*, in *Handbook of Emotion Regulation*, J.J. Gross, Editor 2007, Guilford Press: New York, NY. p. 87-109.
5. Kalisch, R., *The functional neuroanatomy of reappraisal: time matters*. Neuroscience and Biobehavioral Reviews, 2009. **33**(8): p. 1215-26.
6. McRae, K., B. Ciesielski, and J.J. Gross, *Unpacking cognitive reappraisal: goals, tactics, and outcomes*. Emotion, 2012. **12**(2): p. 250-5.

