symptoms will not have to reach diagnosable levels of Major Depressive Disorder to qualify for the study. The non-clinical control group will have minimal symptoms on the BDI-II and State/Trait scales. Participants in each of these study groups then will be randomized into two conditions ($n=10$), each of which will receive 2 assessment/MRI appointments along with 6 sessions of guided practice/training in either 1) Re-interpretation or 2) Mindfulness ER techniques. If randomized into the CBT-based regulation training, subjects will be trained to use a cognitive strategy that instructs them to reappraise situations in positive or less negative ways. If randomized into the MBT-based regulation training, subjects will be trained to use a mindfulness strategy that instructs them to notice and accept their feelings without judgment or intent to act upon them. In both conditions subjects will be shown pictures of negative-affective stimuli and asked to use the strategy over and over again. These appointments will take place 'virtually' using a laptop computer that is set up at the participants house and is controlled remotely by Olin NRC staff. The training sessions will then be monitored by the research assistant via Skype, so that the participant can be given instructions and supervised while completing each session. "Training" in this context is conceptualized as the cumulative amount of practice, with the expectation that greater practice leads to greater mastery. Immediately after the first and sixth practice sessions, participants also will undergo fMRI so that brain function relative to that stage of practice can be assessed. In brief, training will be guided-practice sessions where examples of ER tactics are explained, modeled, then practiced with interactive discussion and feedback. To clarify, the primary outcomes for this pilot study will be fMRI-assessed brain function data, examined either to detect any changes in activation amplitude ("level of activity") in *a priori* ER-linked brain regions-of-interest (ROIs) (Table 1) or changes in the degree of functional connectivity among them. Secondary outcomes will be the BDI-II and STAI. Because we have a well-established infrastructure that includes many other datatypes useful for emotion-related neuroscience, we also will collect a variety of other individual-level data for exploratory analyses. By design, we propose to cast a wide net to collect information on the most relevant factors suggested by prior research to be explored. All data collection methods are described next, followed by a brief data analysis plan.

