ER Practice Sessions During each of the 6 practice sessions, participants will undergo guided instruction with research staff. They will focus only on decreasing emotion to negative stimuli, using whichever of the two emotion regulation strategies they are assigned to learn. In each section, 25% of the stimuli will serve as a control similar to the fMRI task when they are simply asked to view the picture and let their emotional reaction unroll naturally. On the other 75%, they will be guided in how to use their re-appraisal or mindfulness strategy. Practice will consist of guided instruction, question/answer about their attempted techniques, and use of examples for each stimulus if necessary. An important component of practice is continual reminders and examples for how to use the strategy in real-life situations outside the experimental setting with the exact stimulus they are practicing with. Prior research has shown that implementation instructions enhance generalization and rapid acquisition of emotion regulation skill. Each practice session will last between 45-60 minutes over the three-week practice period. Importantly, the stimuli used for practice are carefully controlled in a way that exposes some pictures repeatedly, while others remain relatively novel. At the end of the final appointment, participants will be tested on each category to tease out any effects of exposure to pictures

Table 4. Emotion Test Battery

Task Name	Domain	Min
Cognitive ER Questionnaire ⁷³	Typical ER following negative events	5
Emotion Regulation Questionnaire ⁷⁴	Habitual use of cognitive re-appraisal or suppression for + and - emotions	3
Beliefs of Self-Control Assessment ⁷⁵	39-item self-report measure of emotion sensitivity, intensity, and persistence	5
Five Facets of Mindfulness Questionnaire ⁷⁶	21-item self-report measure of the key elements of mindfulness	5
Emotional Reactivity Scale ⁷⁷	21-item self-report measure of emotion sensitivity, intensity, and persistence	5
Profile of Mood States 2 ⁷⁸ Short Form	Mood before and after ER training	5-10
Beliefs About Will Power Scale	Self-reported traits relating to willpower	3
Emotion Impulsivity Questionnaire	Newly created scale that measures a tendency to respond impulsively when emotionally aroused	2

versus a generalized effect of improvement in their assigned emotion regulation tactic.

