test a general hypothesis that brain function or functional connectivity will change for the ROIs being studied. Because there will be 8 ROIs, we will consider results when using a Bonferroni-corrected α of .00625. However, because this is a pilot study, that correction will not be strictly imposed; rather, its use primarily will help us to decide whether any preliminary data might be publication-capable. *Supplemental Analyses:* Because this is a pilot study, we plan to assess the relationship of fMRI-measured ER brain function change throughout training to numerous other factors. Foremost, we need to evaluate whether non-neural measures of emotional function are altered by the ER training. We will use repeated-measures ANOVA to assess whether or not self-ratings of emotional intensity, SCR, pupil size/fixation time to emotional stimuli change across the fMRI sessions. We also will assess if POMS-2, BDI-II or STAI scores collected at baseline and in the final session differ, as these are clinically-relevant indicators of change that is independent of the ER training itself. Typically in this sort of fMRI experimentation, the degree of change in these measures also is correlated with the degree of change in any brain regions found in the primary analysis to bolster the case of the potential clinical relevance of the findings in *post hoc* analyses.

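### The end-of-training picture test includes no never-practised pictures, so it does not cleanly separate picture exposure from generalised skill

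*Combined protocol and SAP*

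**What the plan says.** All of this is in the combined protocol and SAP.

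- **Picture categories** (ER Practice Sessions): "the stimuli used for practice are carefully controlled in a way that exposes some pictures repeatedly, while others remain relatively novel".
- **The test** (same section): "At the end of the final appointment, participants will be tested on each category to tease out any effects of exposure to pictures". The sentence resumes after Table 4: "versus a generalized effect of improvement in their assigned emotion regulation tactic".
- **Coaching** (same section): participants receive reminders and examples for using the strategy in daily life "with the exact stimulus they are practicing with".
- **View-only trials in practice** (same section): "25% of the stimuli will serve as a control similar to the fMRI task". The section does not say that these trials are crossed with the exposure categories or that they appear in the final test.
- **Amount of practice** (Approach): "6 sessions of guided practice/training". The number of times any one picture is shown is not given.
- **Analysis** (Analysis Plan): the core model is ER group by training timepoint. The supplemental paragraph says "We will use repeated-measures ANOVA to assess whether or not self-ratings of emotional intensity" and the physiological and gaze measures differ between the two scans. Neither model has an exposure-category factor, and no analysis or decision rule is given for the final picture test.

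The documents describe no set of pictures kept out of practice, no earlier test of the same categories, and no rule for matching pictures or assigning them to categories.

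**The concern.** The test is there to answer one question: have participants become used to particular pictures, or have they acquired a skill that carries over to other pictures? Only pictures that were never shown or coached answer it directly. The two categories described differ in how much exposure they had, not in whether they had any.

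Two things follow. First, any habituation from the first exposures is present in both categories. It cancels from the comparison, and good performance on the less-exposed pictures can be taken for skill. Second, the coaching is tied to individual pictures, so even a lightly practised picture may carry a rehearsed response of its own. That is learning about the picture, not general skill.

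The stated aim of the pilot is to see how familiarity with, or mastery of, regulation skills alters brain function, and to inform larger grant proposals. A check that mixes familiarity with mastery would pass that ambiguity on to the next study.

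**Working it through.** The plan gives no figure for this test, so there is nothing to reproduce. The check has a logical part and an illustration of size.

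**1. What the contrast contains.** Write the fall in negative response at the end of training as:

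- repeated set: S + h(b) + c₁
- less-exposed set: S + h(a) + c₂

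S is generalised skill. h(j) is habituation plus picture-specific learning after j exposures. a < b are the exposure counts. c₁ and c₂ are the effects of picture content.

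The difference is h(b) − h(a) + (c₁ − c₂). Content aside, that is the effect of the *extra* exposures. The result on the less-exposed set is S + h(a) + c₂, so it equals skill plus content only if h(a) = 0. A never-practised set has a = 0, hence h(0) = 0.

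**2. How large h(a) might be.** The documents give six practice sessions. Everything else here is assumed:

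- the repeated pictures are seen once per session, so b = 6;
- the less-exposed pictures are seen once or twice, so a = 1 or 2;
- each exposure leaves a fraction r of the previous response, with r from 0.7 to 0.9, so h(j) = 1 − r^j;
- there is no recovery between sessions.

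Share of the repeated set's habituation that is also in the less-exposed set = (1 − r^a) / (1 − r^6).

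| r | 1 − r^6 | a = 1 | a = 2 | a = 0 |
|---|---|---|---|---|
| 0.9 | 0.469 | 0.100/0.469 = 21% | 0.190/0.469 = 41% | 0% |
| 0.8 | 0.738 | 0.200/0.738 = 27% | 0.360/0.738 = 49% | 0% |
| 0.7 | 0.882 | 0.300/0.882 = 34% | 0.510/0.882 = 58% | 0% |

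For a once-seen set the share is roughly 20% to 35%.

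**3. Picture content.** If, and only if, each picture stays in the same category for every participant and the sets are unmatched, the difference between two set means has SD s√(2/m). Here s is the between-picture SD and m the number of pictures per set. With an assumed s = 0.5 rating points:

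- m = 10: 0.5 × √(2/10) = 0.22 points
- m = 20: 0.5 × √(2/20) = 0.16 points

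This difference can have either sign. Rotating pictures across categories between participants averages it out.

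**The case against.** The strongest case on the other side has five parts.

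- **The contrast is informative.** A reader might infer that the test cannot show generalisation at all. The documents do not support that. More against less exposure is a dose comparison, and if the less-exposed pictures are seen once or very late, little habituation may remain. What is missing is the zero-exposure anchor.
- **Pictures may already be matched or rotated.** The plan says that exposure is controlled but not how. Fixed, unmatched lists are neither stated nor excluded, so the content problem is conditional, and it need not favour skill.
- **The analysis is not stated.** A reader might take the repeated-measures ANOVA under Supplemental Analyses as the analysis of this test, object that it treats pictures as fixed, and attach an inflated false-positive rate. That ANOVA concerns change between the two scans. Any such rate would belong to a test that the plan does not specify and to picture lists that it does not describe. The supportable point is that no analysis is given.
- **A view-only condition exists.** If view-only pictures were crossed with exposure category in the final test, regulate minus view would remove passive habituation common to both instructions. The plan does not say that they are. The subtraction would still leave coached, picture-specific responses in place.
- **Other data may bear on generalisation.** The fMRI task collects ratings under Reappraise, Accept and Look. If its pictures do not overlap with the practice pictures, those ratings are relevant too. The documents do not say whether they overlap.

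These points limit the claim to what the test can separate. They do not supply a never-practised comparison.

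**Conclusion.** The point holds in a limited form. As described, the test shows the effect of additional exposure but does not cleanly separate exposure, or picture-specific coached responses, from generalised skill. The ambiguity runs one way for residual habituation, which can be read as skill. It can run either way for picture content.

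The size cannot be known from the documents. The 21% to 34% for a once-seen set, and 41% to 58% for a twice-seen set, rest wholly on assumed exposure counts and habituation rates and ignore recovery between sessions. They show that the leftover could matter, not that it does.

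This is a supplementary check. The Approach section makes fMRI activation or connectivity the primary outcome and the BDI-II and STAI secondary, so the primary analysis does not depend on it. It ranks as a cheap improvement worth making, of low severity.

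**What to change.** 1. Add to the final test a set of never-practised pictures, matched to the other two sets on normative ratings and shown under both regulate and view instructions. Define the generalised effect on that set as regulate minus view.
2. Rotate pictures across the repeated, less-exposed and never-practised categories between participants, so that a category difference cannot be a picture-content difference.
3. State the number of exposures per picture in each practice category, and whether the fMRI-task pictures overlap with them.
4. State the analysis: trial-level ratings, with fixed effects for category, instruction and training group, and random effects for participant and picture.
5. Because no earlier test of these categories is described, say what the final result is compared with before it is called improvement.

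The cost is some extra pictures, rotated lists in the presentation software, and a few minutes at the last appointment. The lists must be settled before the first practice session, because a participant's exposure history cannot be rebuilt afterwards.
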